5.1 Visit Schedule Summary

5.1.1 Screening Period

(Visit 1: Between Day -7 to Day 1)

Before screening assessments are conducted, the patient must be given a complete explanation of the purpose and evaluations of the study. Subsequently, the patient must sign and receive a copy of the ICF that was approved by the Independent Ethics Committee (IEC) and an authorization for

use and disclosure of protected health information before any study-specific procedure is performed. An original signed consent form will be retained in the patient's source documentation at the study site, and a copy will be provided for the patient to take home. Screening will occur within 7 days before treatment administration. Potential patients will be evaluated for entry into the study according to the stated inclusion and exclusion criteria. Individuals who are identified during this screening as not eligible for study enrollment need not complete all screening procedures. The reason for ineligible status will be recorded. Re-screening of patients is permissible if they fulfill the inclusion and exclusion criteria.

The following procedures will be performed to assess the patient's eligibility for the study:

- Explain the nature of the study and have subjects to read and sign an informed consent form
- Assign subject identifier - screen number
- Obtain demographic characteristics and vital signs
- Perform Physical examinations
- Perform foot X-Rays
- Perform assessment of target diabetic foot status
- Perform assessment of foot ulcer status and photography
- Standard ulcer care
- Record medical history including specific chronic complications
- Perform laboratory tests including hematology and biochemistry
- Perform pregnancy test for women of childbearing potential only
- Perform 12 Lead Electrocardiogram (ECG)
- Screen subject for inclusion/exclusion criteria
- Record medical history and concomitant medications

5.1.2 Baseline Visit

(Visit 2: Day 1)

The following procedures will be performed in this visit:

- Confirm subject eligibility
- Obtain the assignment of randomized study treatment (ON101 cream or Aquacel® Hydrofiber® dressing)
- Assign subject identifier - randomization number

- Apply test medication or comparative intervention according to randomization result
- Perform physical examinations and obtain vital signs
- Perform assessment of foot ulcer status and photography
- Standard ulcer care
- Perform assessment of adverse events
- Record medical history and concomitant medications

5.1.3 Comparative Period

(Visit 3-Visit 10: Day 15 to Day 113)

The following procedures will be performed in this period:

- Apply test medication or comparative intervention

If complete wound healing by the judgment of independent reviewer happens before Visit 10, the applied test medication (ON101 cream) or comparative intervention (Aquacel® Hydrofiber® dressing) will be stopped at next scheduled visit which will be deemed as V10.

If the wound is unhealed at Visit 10, only Aquacel® Hydrofiber® dressing will be applied.

- Perform physical examinations and obtain vital signs
- Perform laboratory tests including hematology and biochemistry at Visit 4, Visit 6, Visit 8, Visit 10 and at the visit of early permanent discontinuation of study treatment
- 12 Lead ECG examination will be performed at Visit 10 or at the visit of prematurely discontinuation of study treatment
- Perform assessment of foot ulcer status and photography
- Standard ulcer care
- Perform assessment of adverse events
- Record concomitant medication

5.1.4 Follow-up Period

(Visit 11-Visit 14: Day 127 to Day 197)

The following procedures will be performed in this period:

- Apply Aquacel® Hydrofiber® dressing to the subjects whose wounds are unhealed or recurrent
- Perform physical examinations and obtain vital signs

- Laboratory tests including hematology and biochemistry will be performed at Visit 14 (Week 28) or Visit of early permanent discontinuation during the follow-up period
- 12 Lead ECG examination will be performed at visit 14 (Week 28) or visit of early permanent discontinuation during the follow-up period
- Perform assessment of foot ulcer status and photography
- Standard ulcer care
- Perform assessment of adverse events
- Record concomitant medication

5.2 Dosing and Administration of Study Treatments and Other Medications

5.2.1 Dose/Dose Regimen and Administration Period

The investigator will select the treatment area for each subject at the baseline visit. During the treatment period, subject will apply the study medication (ON101 cream) to the selected treatment area only. The study cream will be applied two times daily for a maximum period of 16 weeks, until the wound/ulcer closure (wound size of 0) for two consecutive visits at least 2 weeks apart, or until the study subject exited the study as lack of efficacy satisfactory (defined as a worsening of Wagner grade to level of 3).

The surface area of the ulcer will be estimated at each clinical visit in the following manner. Length is the longest edge-to-edge measurement of the ulcer; width is taken from a perpendicular axis to the length. The study drugs will be applied in an amount to fully cover the ulcer area. The maximum amount of ON101 cream applied on the wound must not exceed 2 millimeter in thickness (or 1 cc for ulcer size of 5cm²). The investigator/study coordinator will give a demonstration and will train the patients how to apply the medication at each clinical visit.

Aquacel[®] dressing offers the unique gelling action of Hydrofiber[®] technology that absorbs and locks in exudate and bacteria. It provides excellent absorption and retention capabilities for moderate to highly exuding wounds, conforms to the wound surface to form an intimate contact, supporting wound healing by providing a moist wound healing environment. The Aquacel[®] Hydrofiber[®] dressing will be left in place for up to 7 days or changed earlier, depending on the extent of the exudate produced by the wound.

Both treatment groups will be covered by several layers of gauze, and subjects received accommodative footwear for non-plantar ulcers and off-loading for plantar ulcers to relieve the pressure from the ulcerated foot; the products used are not specified.

5.2.2 Previous and Concomitant Medication (Drugs and Therapies)

5.2.2.1 Previous Medication (Drugs and Therapies)

All previous medications, which are used within 4 weeks prior to the randomization, will be recorded in the source documents and CRF.

5.2.2.2 Concomitant Medication (Drugs and Therapies)

If the administration of any concomitant treatment becomes necessary, it must be reported in the case report form and in the subject's medical records. As far as possible, minimum changes (dose, frequency) should be made to the concomitant treatment during the study. However, concomitant medications should be kept to a minimum during the study. The sponsor must be consulted if there is any doubt, and a decision to withdraw the subject must be made jointly by the sponsor and the investigator.

Permitted concomitant medication

Oral and/or intravenous antimicrobial agents are allowed for treatment of presumed infection.

Prohibited concomitant medication

Topical antimicrobials and agents known to affect wound healing are not allowed during the study treatment period.

5.2.3 Treatment Compliance

The amount of returned study medication (ON101) from each subject will be recorded in the CRF at each visit.

5.2.4 Emergency Procedures and Management of Overdose

No specific advice is available for treatment of overdose of ON101, other than supportive treatment. No specific antidote has been identified to date.

In emergency situations during study, the investigator will perform adequate procedures to ensure the health and safety of study subject. All emergencies and serious adverse events should be reported by telephone immediately to Sponsor.

5.2.5 Restrictions During the Study

Subjects shall prevent from causing any pregnancy during the study period.

If any treatment (drugs, therapies) becomes necessary, subjects should inform study site before receiving treatment and ask the Investigator or sub-investigator for their instructions.

5.3 Demographics and Baseline Characteristics

5.3.1 Demographics

The following demographic data will be collected at screening.

- Sex
- Birthday
- Height, body weight
- Ankle-brachial index on target foot, determined by dividing the highest ankle systolic measure by the highest brachial systolic measure
- Diabetes type and duration
- History of previous medications and therapies (within 4 weeks prior randomization)
- History of smoking and alcohol use

Baseline characteristics will be collected at Screening or on Day 1 (before administration of study intervention) in accordance with the schedule as detailed in the Schedule of Assessments.

5.3.2 Medical History

A complete medical history will be recorded in the source documents and CRF. All details (including information related to the duration, i.e., the number of months or years), especially those regarding chronic and recurring illness will be recorded on the medical history page with special emphasis on medical history of the last 12 months prior to randomization. In addition, the following history on chronic complications will be collected separately: coronary artery disease (CAD), diabetic neuropathy (DN), diabetic kidney disease (DKD), diabetic retinopathy (DR), diabetic peripheral arterial disease (PAD).

5.3.3 Diagnosis of the Target Disease, Severity, and Duration of Disease

Please refer to “Diabetic Foot Disorders: A Clinical Practice Guideline (2006 revision)” as Appendix 1.

The following target ulcer characteristics should be collected before randomization:

- Duration of diabetic foot ulcer
- Ulcer severity (Wagner grade)
- Ulcer etiology (Neuropathic, Neuro-ischemic)
- Ulcer location (Plantar, Non-plantar)

Although no single system has been universally adopted, the classification system most often used was described and popularized by Wagner. In the Wagner system, foot lesions are divided into six grades based on the depth of the wound and extent of tissue necrosis.

Grade 0: No open lesion, may have deformity or cellulitis

Grade 1: Superficial ulcer

Grade 2: Deep ulcer to tendon or joint capsule

Grade 3: Deep ulcer with abscess, osteomyelitis, or joint sepsis

Grade 4: Local gangrene – forefoot or heel

Grade 5: Gangrene of entire foot

The major aetiologies of DFUs are neuropathy (nerve damage), neuroischaemia and peripheral vascular (arterial) disease. Some 40–70% of DFUs are caused by neuropathy, 15–24% by peripheral vascular disease and 15–45% by neuroischaemia.

The neuropathic foot is typically warm to touch with good perfusion and palpable pulses. The skin may be anhydrotic (dry) and prone to fissuring and callosities. Ulcers often occur on the plantar surface, principally under the metatarsal heads in the forefoot. They are round and surrounded by callus.

The neuroischaemic foot is typically cool to touch and has poor perfusion, characterized by diminished or absent foot pulses. The skin is usually atrophic, anhydrotic and shiny. Hair growth is often minimal and atrophy of the subcutaneous tissues is apparent. Ischaemic ulcers often occur on the digits and heels, and are usually dry with vertical walls. Necrotic tissue may be present.

5.4 Efficacy Assessment

The efficacy assessment is based on the subject's wound size. It will be conducted at clinic by digital planimetry method at baseline and every 2 weeks after study intervention until wound closure (wound size of 0) has confirmed 2 weeks apart, or until the study subject exited the study as lack of efficacy satisfactory.

The digital planimetry method involves applying a two-layer transparent acetate over the wound and tracing the perimeter with a permanent pen. The contact layer is then discarded into clinical waste and the top layer stored within the subject notes. The top layer is placed on a digital tablet, and the border is re-traced using a stylus. The underlying sensor then calculates the wound area.

For the purpose of this study a complete healing will be defined as complete epithelialization which is maintained with no drainage for at least 2 weeks and is confirmed by a blinded independent evaluator. At each clinic visit after study intervention, digital photographs should be taken of study wound after the area had been carefully shaved to visualize the wound margin and for better visualization of epithelialization and granulation tissue area.

5.5 Safety Assessment

5.5.1 Vital Signs

Vital signs (including temperature, blood pressure, heart rate and respiratory rate, all measured after 5 minutes in the sitting position) and weight will be taken at each scheduled visit or early permanently discontinued study intervention. The subject's height will be recorded at the baseline visit. Significant adverse changes in vital signs occurring after the subject randomized into this study will be recorded as adverse events.

5.5.2 Adverse Events

Adverse event collection will begin after study intervention initiated and continue through the entire study visit. All observed or spontaneously reported AEs will be recorded in the source documents and CRFs. Data to be recorded includes a description of the event, date of onset and end of the event, severity, action with respect to study intervention, treatment required, relationship to study intervention, and outcome of the event.

5.5.3 Laboratory Assessments

Blood samples for the laboratory tests will be collected at specified visit, i.e., Screening, Week 4, Week 8, Week 12, Week 16, Week 28 or early permanently discontinued study intervention. All the measurements will be conducted in the laboratory at the study site.

Laboratory reports must be signed and dated by the principal investigator or sub-investigator indicating that the report has been reviewed and any abnormalities have been assessed for clinical significance. A clinically significant laboratory abnormality that has been verified by retesting will be followed until the abnormality returns to an acceptable level or a satisfactory explanation has been obtained.

The following is a list of laboratory evaluations to be performed during the course of the study according to the local laboratory instructions.

Hematology: hemoglobin, white blood cell (WBC) count total and differential, platelet count, red blood cell (RBC)

Biochemistry: glycated hemoglobin (HbA1c), serum glutamyl-oxaloacetic transaminase (AST), serum glutamic-pyruvic transaminase (ALT), albumin, creatinine, blood urea nitrogen (BUN), fasting plasma glucose

Urine or serum pregnancy test will be performed on women with child bearing potential at screening visit.

Note: According to the changing of regional practice, the BUN test can't be conducted in local laboratory in Mainland China. The BUN test will be waived in Mainland China.

5.5.4 Physical Examination

A physical examination including vascular, neurological, and musculoskeletal status will be performed at screening, baseline visit, each bi-weekly visit (during comparative period), and scheduled visits during follow-up period.

5.5.5 Electrocardiogram (ECG)

An ECG will be performed at screening, week 16 and week 28 or early permanently discontinued study intervention.

5.5.6 X-ray

The foot X-ray will be performed at screening visit.

5.6 Adverse Events and Other Safety Aspects

5.6.1 Definition of Adverse Events (AEs)

An adverse event (AE) is defined as any untoward medical occurrence in a subject administered a study treatment and which does not necessarily have a causal relationship with this treatment. An AE can therefore be any unfavorable and unintended sign (including an abnormal laboratory finding), symptom, or disease temporally associated with the use of a study treatment, whether or not related to the study treatment.

An abnormality identified during a medical test (e.g., laboratory parameter, vital sign, ECG data, physical exam) should be defined as an AE only if the abnormality meets one of the following criteria:

- Induces clinical signs or symptoms
- Requires active intervention
- Requires interruption or discontinuation of study treatment
- The abnormality or investigational value is clinically significant in the opinion of the investigator.

Beginning when the subject randomized, the investigator will closely monitor each subject for evidence of treatment intolerance and for the development of clinical or laboratory evidence of adverse events.

Whenever possible, diagnoses should be given when signs and symptoms are due to a common etiology (e.g., cough, runny nose, sneezing, sore throat, and head congestion should be reported as “upper respiratory infection”).

5.6.2 Definition of Serious Adverse Events (SAEs)

A serious AE is any untoward medical occurrence that at any dose:

- Results in death,
- Is life threatening (an event in which the <subject> is at risk of death at the time of the event; it does not refer to an event which hypothetically might have caused death if it was more severe),
- Results in persistent or significant disability/incapacity,
- Results in congenital anomaly, or birth defect,
- Requires inpatient hospitalization or leads to prolongation of hospitalization (hospitalization for treatment/observation/examination caused by AE is to be considered as serious).
- Other medically important events.

Medical and scientific judgment should be exercised in deciding whether expedited reporting is appropriate in other situations, such as important medical events that may not be immediately life-

threatening or result in death or hospitalization but may jeopardize the subject or may require intervention to prevent one of the other outcomes listed in the definition above. These events, including those that may result in disability, should also usually be considered serious. Examples of such events are intensive treatment in an emergency room or at home for allergic bronchospasm; blood dyscrasias or convulsions that do not result in hospitalization; or development of drug dependency or drug abuse.

The cause of death of a subject in a clinical study, whether or not the event is expected or associated with the investigational agent, is considered a serious adverse event. Any event requiring hospitalization (or prolongation of hospitalization) that occurs during the course of a subject's participation in a clinical study must be reported as a serious adverse event.

5.6.3 Criteria for Causal Relationship to the Study Treatment

The investigator will also evaluate the relationship of each adverse event to study intervention according to the definitions as follows. Adverse events that fall under either "Unlikely", "Possible" or "Probable" or "Definitely" should be defined as "adverse events whose relationship to the study treatments could not be ruled out".

- Not related: Adverse reactions associated with drug usage are clearly not related.
- Unlikely: Adverse reactions and drug usage on the timing is not reasonable (but not impossible), and the patients' own illness or medicines (chemicals) indicated more reasonable explanation for this event.
- Possible: A clinical event, including laboratory test abnormality, with a reasonable time sequence to administration of the drug, but which could also be explained by concurrent disease or other drugs or chemicals. Information on drug withdrawal may be lacking or unclear.
- Probable: A clinical event, including laboratory test abnormality, with a reasonable time sequence to administration of the drug, unlikely to be attributed to concurrent disease or other drugs or chemicals, and which follows a clinically reasonable response on re-administration (rechallenge) or withdrawal (dechallenge).
- Definitely: Adverse reaction associated with medication usage is time sequential, which is credible and cannot be reasonably counted to the patients' own illness or medicines (chemicals). The reaction after stopping the medication reflects the credible basis on pharmacology or pathology, as well as precise pharmacological phenomena or disease state, it appears similar reaction if re-dosing.

5.6.4 Criteria for Defining the Severity of an Adverse Event

The following standard with 3 grades is to be used to measure the severity of adverse events, including abnormal clinical laboratory values.

- Mild: No disruption of normal daily activities
- Moderate: Affect normal daily activities
- Severe: Inability to perform daily activities

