3.3 Exclusion Criteria

Subject will be excluded from participation if any of the following apply:

1. Presence of necrosis, purulence or sinus tracts that cannot be removed by debridement
2. Acute Charcot's neuroarthropathy as determined by clinical and/or radiographic examination

3. Has undergone revascularization procedure aimed at increasing blood flow in the treatment target limb < 4 weeks prior to randomization
4. Poor nutritional status defined as an albumin < 2.5 g/dL
5. AST and/or ALT >3 × the normal upper limit
6. Serum Creatinine >2 × the normal upper limit
7. Treatment with immunosuppressive or chemotherapeutic agents, radiotherapy or systemic corticosteroids within the 4 weeks before randomization
8. Use of any investigational drug or therapy within the 4 weeks prior to randomization
9. A psychiatric condition (e.g., suicidal ideation), current or chronic alcohol or drug abuse problem, determined from the subject's medical history, which, in the opinion of the Investigator, may pose a threat to subject compliance
10. Judged by the investigator to be not suitable for the study for any other reason

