7.5 Analysis of Safety

Adverse events will be regarded as Treatment Emergent (TEAE) if they started on or after the date and time of administration of the first dose of study intervention or if they were present prior to the administration of the first dose of study intervention and increased in severity during the study.

Adverse Events (AEs) will be coded using the standard Medical Dictionary for Regulatory Activities (MedDRA) dictionary and grouped by system organ class and preferred term and events. TEAEs will be summarized by frequency and proportion of total subjects, by system organ class and preferred terms. If appropriate, the incidence of adverse events (preferred terms and system organ class) will be compared for each of the two treatment groups using Fisher's exact test.

For the clinical laboratory and vital signs data, the data will be tabulated by treatment group for raw data and for change from baseline to evaluated time points; descriptive statistics to be provided include: n, mean, median, standard deviation, minimum and maximum. The differences between groups will be analyzed by analysis of covariance (ANCOVA) with factor being fitted for treatment, and baseline value fitted as a covariate. Subjects with laboratory data outside the normal range will be listed and abnormal values will be flagged.

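### Laboratory adverse events are graded only by effect on daily activities, so symptom-free ones are always mild, and symptom-free worsening of an entry abnormality cannot meet the increased-severity route to a TEAE

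*Combined protocol and SAP*

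**What the plan says.** Section 5.6.4 gives the only severity scale in the text, and it "is to be used to measure the severity of adverse events, including abnormal clinical laboratory values". The grades are "Mild: No disruption of normal daily activities", "Moderate: Affect normal daily activities" and "Severe: Inability to perform daily activities". No grade refers to the size of a laboratory value.

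Section 7.5 gives two routes to treatment-emergent status. The new-onset route covers events that "started on or after the date and time of administration of the first dose of study intervention" and has no severity condition. The second route covers events already present before the first dose "and increased in severity during the study".

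Section 3.3 excludes subjects only at "AST and/or ALT >3 × the normal upper limit" and "Serum Creatinine >2 × the normal upper limit", so values above normal but within those limits may enter.

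Three other sections bear on the point:
- Section 5.6.1 makes a test abnormality an adverse event on any one of four criteria. The investigator's judgement of clinical significance is enough, and symptoms are not required.
- Section 5.5.2 starts adverse event collection only once treatment has begun.
- Section 7.5 also plans descriptive statistics by arm for raw values and changes (including median, minimum and maximum), ANCOVA on change, and a listing of out-of-range subjects with flags.

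**The concern.** Changes in creatinine, AST, ALT or albumin can be large without affecting what a person does in a day. A scale built only on daily activities cannot rank such changes. The same scale feeds the increased-severity route in section 7.5, so a flaw in grading becomes a flaw in counting.

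Laboratory abnormalities are named in the additional (safety) objective in section 2.1. At stake is whether the safety report can show how large the laboratory changes were, and whether worsening from an abnormal start is counted in the same way across sites and arms. The count depends partly on an investigator who knows the allocation (section 4.4). Only the photograph evaluator is blinded.

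**Working it through.** The plan states no figure on this point, so there is none to reproduce. The check applies the definitions to the possible cases.

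**Step 1: grading.** Moderate and severe both require an effect on daily activities. A symptom-free laboratory event has none, so it is mild at any size.

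**Step 2: TEAE status.** The values in cases b and c are assumed for illustration.
- a. Normal at entry, then a symptom-free rise judged clinically significant: mild, and a TEAE by new onset. It is counted, but its size is lost.
- b. Creatinine 1.8 × ULN at entry, rising to 4 × ULN without symptoms, treated as a continuing condition: mild before and after. The increased-severity route is not met, so it is not a TEAE.
- c. The same subject, but the rise is recorded as a new adverse event because it first meets section 5.6.1 after dosing: a TEAE by new onset, graded mild.
- d. Abnormal at entry, and the worsening affects daily activities: the grade rises and the increased-severity route is met.

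Cases b and c have identical data and opposite results. Nothing in the documents chooses between them.

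**Step 3: the starting grade.** The increased-severity route compares severity before and after the first dose. Section 5.5.2 collects no adverse events before treatment, so no pre-dose grade is defined for that comparison.

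**Step 4: the other laboratory outputs.** Assume 5% of one arm rises from 1.5 to 4 × ULN.
- Subjects: 0.05 × 118 = 5.9, about 6.
- Rise per subject: 4.0 − 1.5 = 2.5 × ULN.
- Shift in arm mean: 0.05 × 2.5 = 0.125 × ULN.
- If only one subject rises: 2.5 / 118 = 0.021 × ULN.

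The maximum is 4 × ULN with one such subject or with six. It reveals that an extreme value exists, but not how many. An out-of-range flag marks 1.5 and 4 × ULN alike. A reader could count from the listing by hand, but no by-arm count is planned.

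**Step 5: how many subjects could be in case b or c.** The documents give no distribution of entry values. If 10% to 30% of the 236 enter abnormal but within the limits (assumed), that is 0.10 × 236 = 23.6 to 0.30 × 236 = 70.8, or about 24 to 71 subjects. These are subjects in whom the problem could arise, not subjects expected to worsen.

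**The case against.** The strongest reply is that little is actually lost:
- A worsened entry value can still be a TEAE by new onset, because collection starts after treatment and clinical significance alone makes an adverse event.
- Section 5.5.3 requires the principal investigator or a sub-investigator to sign every laboratory report and assess abnormalities. Verified significant ones are followed up.
- The maximum by arm and the flagged listing would expose an extreme rise.
- Section 5.6.2 judges seriousness separately from severity, so a mild grade does not block SAE reporting.
- Section 7.2 defers detail to a separate SAP, whose text is not in the supplied document and which may contain shift tables.
- Investigators know the allocation for every adverse event, not only laboratory ones.
- Nothing points to a laboratory signal. The product is topical, section 1.3 reports no adverse events caused by it in two earlier trials, and section 1.2 gives a 28-day oral NOAEL in rats of 3000 mg/kg/day.

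Most of this stands, and it limits the point. It does not remove it. The new-onset route depends on a choice that the plan leaves open. The signed review governs capture but does not change the grade. A separate SAP could add tables, but the severity grade comes from the protocol's scale. The absence of an expected signal lowers the priority without making the scale able to detect one.

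**Conclusion.** The point holds in a limited form. Every symptom-free laboratory adverse event is mild whatever its size. Symptom-free worsening of an abnormality present at entry cannot meet the increased-severity route. Whether it counts as a TEAE by the other route is left to the investigator without a rule.

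A reader might infer more, and the documents do not support it:
- That no worsening of an entry abnormality can be a TEAE. This fails for worsening that affects daily activities and for events recorded as new.
- That large rises would be hidden. The maximum and the flagged listing would show them.
- That kidney disease is expected in this population. Section 5.3.2 collects its history but says nothing of its frequency.

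The conclusion on definitions needs no numerical assumption. The figures of 24 to 71 subjects and 0.125 × ULN rest on assumed shares and only illustrate scale. Priority is low to moderate: the primary analysis and SAE reporting are unaffected.

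**What to change.** - **Section 5.6.4:** limit the daily-activity scale to clinical events. Grade laboratory adverse events by size against the local reference range, using a published grading scale or bands named in advance.
- **Section 7.5:** state that a move to a higher laboratory grade than at baseline counts as increased severity, whether the site entered the event as new or continuing, and that each such event is counted once. Name the screening value as baseline, since section 5.5.3 schedules no Day 1 sample.
- **Section 7.5 or the SAP:** add a by-arm baseline-to-worst shift table. Add the number of subjects whose worst post-baseline value crosses the plan's own entry limits (AST/ALT above 3 × ULN, creatinine above 2 × ULN, albumin below 2.5 g/dL). These serve as reporting thresholds only and carry no consequence for treatment.

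The cost is one paragraph, a sentence or two and one table. Values are already collected (section 5.5.3) and sites already supply their normal ranges (section 8.3.2). Section 7.6.2 shows that the first interim analysis has taken place, so the grades should be derived by program for all subjects, including those who have finished. The downside is that more laboratory TEAEs will be reported.
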